5.3. Second-Line Treatment for Glioblastoma

Once patients relapse, several treatments have been used or approved: lomustine (CeeNU®), carmustine (1,3-bis (2 chloroethyl)-1-nitrosourea [BCNU]), including Gliadel® wafers), nimustine (3-[4-amino-2-methyl-5-pyrimidinyl] methyl)-1-(2-chloroethyl)-1-nitrosourea hydrochloride

[ACNU]), TMZ, and bevacizumab (Avastin®, United States [US] and many countries outside the European Union).

Lomustine, an oral nitrosourea agent, has been shown to be useful as a single agent in both primary and metastatic brain tumors. Because of the high lipid solubility and the relative lack of ionization at physiological pH, lomustine crosses the blood-brain barrier quite effectively. Common and severe adverse events (AEs) include bone-marrow suppression (most notably thrombocytopenia and leukopenia). At the time of writing this protocol, lomustine is considered the most accepted second-line treatment in GB.

Enzastaurin and cediranib (AZD2171) were other agents investigated in the same line of treatment and compared to lomustine (Batchelor et al. 2010b; Wick et al. 2010a), but which failed to show an improvement over lomustine treatment ([Table JBAL.5.1](#)).

A number of other chemotherapeutic agents, including erlotinib, cilengitide, carboplatin, irinotecan, or fotemustine (Reardon et al. 2004, 2005, 2008; van den Bent et al. 2009) have been used as salvage therapy either alone or in combination. For patients who progress on TMZ, other combination therapies may be possible. Several recent trials have evaluated various combinations containing angiogenesis inhibitors combined with cytotoxic chemotherapy. Using cytotoxic chemotherapy alone, the PFS-6 rate is about 15% (Wong et al. 1999). Compared to this PFS rate, the combination of bevacizumab with other chemotherapies have been reported to be around 50% (Vredenburgh et al. 2007) and summarized recently in a meta-analysis (Wong et al. 2011) as shown in [Table JBAL.5.1](#).

As a consequence of these responses in second-line treatment, bevacizumab has been approved for recurrent/progressive GB in the US and many other countries outside the European Union (Wick et al. 2010b).

Table JBAL.5.1. Summary of Responses in Second-line Treatment

Compound (total patients)	ORR (95% CI)	SD (95% CI)	OS (95% CI)	PFS (95% CI)	PFS Rate at 6 months (95% CI)	References
Bevacizumab						

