8.2. Discussion of Design and Control

CCI patients will be entered in order to randomly assign **CCI** patients to 1 of 3 treatment arms using a **CCI** allocation ratio in favor of the LY2157299 plus lomustine arm. A randomized, controlled design is being used in this study. Randomization minimizes systematic bias in the selection and assignment of patients to study therapy and provides justification for inferential statistical methods to be used on data from this study. The study will use dynamic randomization for the known influence factors, such as age, PS, and primary or secondary GB.

Using an appropriate concurrent control arm (which is lomustine in combination with placebo) enables direct statistical estimation of benefits and harms due to study therapy and minimizes bias in the assessment and interpretation of observed treatment effects. The rationale behind favoring the combination arm in the randomization is that this is the primary treatment of interest to compare with lomustine alone. However, since there was some evidence of activity in patients with GB in Study JBAH where LY2157299 was administered as a monotherapy, there is medical interest in getting more information in terms of efficacy and safety for LY2157299 monotherapy. Therefore, a monotherapy arm is also included.

Since OS is not affected by pseudoprogression evaluations, OS is a preferred primary endpoint over PFS. A Bayesian design can be used to leverage survival data for lomustine alone from

historical clinical trials in order to benefit from the **CCI** randomization of the combination arm relative to lomustine alone with the goal of increasing power over an otherwise similar design.

Glioblastoma is a heterogenous tumor entity and treatment effects may be influenced by MGMT methylation, IDH1 gene mutation status, or other genetic differences. Hence, to understand this influence on OS, all patients will be required to provide tumor tissue to determine the genetic make-up of the tumor and its impact on survival.

Poststudy treatment with bevacizumab may affect the OS. Collection of poststudy treatment will be limited to the first new regimen and any new subsequent therapy will not be collected.

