10.1.2. Efficacy Assessments during the Postdiscontinuation Period

After patients have discontinued study treatment, they may receive additional anticancer therapy at the discretion of the investigator.

For those patients who discontinue study treatment without objectively measured progressive disease, the investigative sites will continue to monitor patients approximately every 60 days (± 14 days) to evaluate tumor response by the same method used at baseline and throughout the study, until objective progression or the patient starts a new anticancer therapy.

Once a patient has objective progression or starts a new anticancer therapy, they will be followed for OS approximately every 60 days (± 14 days) until death or study completion.

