12.2.4.2. Postdiscontinuation Regimens

Listings of patients reporting postdiscontinuation therapies will be provided.

Bevacizumab treatment after poststudy drug discontinuation will be listed and included in the OS analyses to detect any potential influence on OS.

Listings will include regimen number indicating which different therapies and/or types of therapies are included in the same regimen. The numbers and percentages of patients reporting postdiscontinuation regimens will be provided overall.

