12.2.7. Additional Efficacy Analyses

Overall survival (OS) is the primary outcome of interest and the primary analysis is as described above.

Overall survival (OS) and OS rate at 12 months will be summarized by treatment arm using Kaplan-Meier estimates of the median survival times (including 95% CIs) to inform assumptions for use in future trial planning (Kaplan and Meier 1958). Additional exploratory analyses using proportional hazards models to control for other factors may be performed, including, but not limited to, adding a covariate indicating the extent of lomustine exposure, PD marker assessment of the tumor tissue, the known influence factors, such as age, PS, and primary or secondary GB and whether patients had poststudy treatment with bevacizumab.

The following secondary efficacy parameters will be summarized for each treatment group:

- PFS distribution parameters and PFS rate
- ORR

Progression-free survival and PFS rate will be summarized (at **CCI** [REDACTED]) using Kaplan-Meier estimates of the median survival times (including 95% CIs) to inform assumptions for use in future trial planning (Kaplan and Meier 1958). Estimates of HRs between

the 3 arms will also be provided. Additional exploratory analyses using proportional hazards models to control for other factors may be performed.

Overall response rate (ORR) and, additionally, disease control rate given the risk of pseudo progression, will be estimated by dividing the total number of responders ([CR or PR] or [CR or PR or SD]) by number of randomly assigned patients. Exact 95% CIs for each treatment arm will be provided.

Additional analyses may be carried out to judge the influence of any patients who did not meet enrollment criteria but were inadvertently enrolled and continued on treatment after obtaining approval from the sponsor and/or patients who have continued treatment after objective disease progression (see Section 7.3.1). A subanalysis will be conducted by excluding such patients to determine their influence on the final study results.

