6.10.3. Secondary Efficacy Analyses/Outcomes/Comparisons

A similar Bayesian analysis as described in [Section 6.10.1](#) will also be carried out to provide the hazard rates and ratios including 90% predictive intervals of the HR between LY2157299 monotherapy and lomustine plus placebo therapy and, between LY2157299 plus lomustine therapy and LY2157299 monotherapy.

Additional exploratory analyses using proportional hazards models to control for other factors may be performed, including, but not limited to, adding a covariate indicating the extent of lomustine exposure, PD marker assessment of the tumor tissue, the known influence factors, such as age, PS, and primary or secondary GB and whether patients had poststudy treatment with bevacizumab.

The following secondary efficacy parameters will be summarized for each treatment group:

- PFS distribution parameters and PFS rate
- ORR
- Disease control rate

Progression-free survival (PFS) and PFS rate will be summarized (at **CCI** [REDACTED]) using Kaplan-Meier estimates of the median survival times (including 95% CIs) to inform assumptions for use in future trial planning (Kaplan and Meier 1958). Estimates of HRs

between the 3 arms will also be provided using proportional hazards models. Additional exploratory analyses using proportional hazards models to control for other factors may be performed.

Overall response rate (ORR) and, additionally, disease control rate given the risk of pseudoprogression, will be estimated by dividing the total number of responders ([CR or PR]) or [(CR or PR or SD)] by number of randomly assigned patients in each treatment group. Exact 95% CIs for each treatment arm will also be provided.

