6.17. Planned Exploratory Analyses

Exploratory analyses on efficacy endpoints such as overall survival or progression-free survival will be carried using data from the treatment arms. Covariates may be added to the time-to-event models to explain the variability in survival times. Selection of covariates will be determined from Cox proportional hazard model. These covariates may include but are not limited to the following prognostic/predictive factors:

- Use of corticosteroids at randomization
- Baseline ECOG performance status
- Age

- Primary or secondary GB
- Post-surgical status (fully resected, partially resected)
- MGMT promoter methylation status, Fox3p+ status
- Baseline biomarker/Biomarker response

Point estimates and 95% confidence intervals for median survival (OS or PFS) may be provided for the model where the prognostic factor is found to influence variability in survival times.

The pharmacodynamic markers that will be evaluated include tumor markers (LDH, S100 β), TGF-beta related markers (TGF-beta1, PF4) and changes in T cell subpopulation (for example T regulatory cells as evaluated by CD4+CD25+Fox3p+ and total concentration in Fox3p).

Pre- and post-dose values of the various biomarkers whose data are continuous will be analyzed using a mixed effects model with time, treatment arm and their interaction as fixed effects and patient as a random effect, after applying appropriate transformation (log scale to concentration data). Least square means (geometric means if log transformation is used) by time and treatment arm together with 90% confidence intervals will be provided. Mean differences (or ratio of means) and 90% confidence intervals between pre- and post-dose timepoints will be estimated from the model.

For biomarkers with categorical data, frequency and percentages will be used to summarize the data.

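### Exploratory OS Cox models may adjust for later bevacizumab with no time-dependent coding stated; read as ever/never, a drug with no effect would look protective

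*SAP*

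**What the plan says.** OS runs from randomization to death (SAP 6.10, Protocol 12.2.6). SAP 6.10.3 lists factors that optional proportional hazards models may control for. Age, performance status and primary or secondary glioblastoma are baseline factors. In the same sentence stands "whether patients had poststudy treatment with bevacizumab". Protocol 12.2.7 has the same list, including "adding a covariate indicating the extent of lomustine exposure". SAP 6.17 adds "Baseline biomarker/Biomarker response" as a possible covariate.

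The protocol treats later bevacizumab as a real issue. Section 8.2 states: "Poststudy treatment with bevacizumab may affect the OS". Section 12.2.4.2 is firmer than the SAP: "Bevacizumab treatment after poststudy drug discontinuation will be listed and included in the OS analyses to detect any potential influence on OS". Section 8.2 also limits the data: "Collection of poststudy treatment will be limited to the first new regimen and any new subsequent therapy will not be collected".

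Neither document says how a covariate that becomes known after randomization enters the model. Post-discontinuation tumor monitoring runs only "until objective progression or the patient starts a new anticancer therapy" (Protocol 10.1.2).

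**The concern.** A patient can be a poststudy bevacizumab user only by living long enough to stop study drug and start it. Patients who die early are never-users by construction. A fixed yes/no flag counted from randomization therefore gives users a stretch of guaranteed survival, and the model attributes it to the drug. The stated purpose, to detect an influence on OS, is then defeated: an inert drug appears beneficial.

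Extent of lomustine exposure has the same structure, because more doses require more time alive and progression-free. On-treatment biomarker response does too, since it needs survival to the assessment.

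At stake is a false statement in the study report that later bevacizumab prolonged survival. If uptake differs between arms, the adjusted treatment hazard ratio is also distorted.

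**Working it through.** **Inputs from the documents.** Median OS on lomustine is 7.1 and 9.8 months in the two historical trials (Protocol Attachment 10). The average reproduces: (7.1 + 9.8)/2 = 8.45, given as 8.5. Median PFS on lomustine is 1.64 months or 82 days (Protocol Table JBAL.5.1), and 82/30.44 = 2.69 months. The survival model is exponential and minimum follow-up is 94 weeks.

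**Assumptions.** Uptake is 10, 30 or 60% of progressors, bevacizumab starts 0.7 months after progression, its true hazard ratio (HR) is 1, and accrual takes 9 months. The number randomized is redacted, so 120 is assumed. Uptake may well vary by country, since "bevacizumab has been approved for recurrent/progressive GB in the US and many other countries outside the European Union" (Protocol 5.3).

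**Hand check: progression neutral for death, no censoring, PFS median 1.64 months.**
- Death hazard: ln2/8.45 = 0.0820 per month, so mean survival is 12.19 months.
- PFS hazard: ln2/1.64 = 0.4227, so the mean time to first event is 2.37 months.
- Progression comes first in 1 − 0.0820/0.4227 = 0.806 of patients. Of these, exp(−0.0820 × 0.7) = 0.944 are alive 0.7 months later.
- At 60% uptake, users are 0.6 × 0.806 × 0.944 = 0.457 of patients.
- Users' mean survival: 2.37 + 0.70 + 12.19 = 15.26 months.
- Never-users' mean survival: (12.19 − 0.457 × 15.26)/0.543 = 9.61 months.
- Ratio of death rates, users to never-users: 9.61/15.26 = 0.63, for a drug that does nothing.

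The same steps give 0.74 at 30% uptake and 0.78 at 10%. With PFS of 82 days they give 0.55, 0.66 and 0.71.

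**Simulated ever/never Cox model, true HR 1.** The ratio is the death hazard after progression to that before it.

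| Uptake | HR, ratio 1 or 2 | HR, ratio 3 to 10 | False significance favouring bevacizumab, ratio 1 to 10, 120 patients |
|---|---|---|---|
| 60% | 0.51-0.68 | 0.67-0.80 | about 20-95% |
| 30% | 0.61-0.79 | 0.77-0.87 | about 8-45% |
| 10% | 0.67-0.82 | 0.81-0.90 | about 3-7% |

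The nominal rate is 2.5%. The delay matters too: 0.25 or 1.5 months instead of 0.7 gives 0.47-0.85 at ratio 1 or 2, and 0.25 months with a 10-fold ratio gives 0.85-0.94.

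**Alternative codings of the same inert drug.**
- Time-dependent bevacizumab without progression in the model: 1.04-1.26 when progression doubles the death hazard, and up to 1.48 in a second set of scenarios at a 3-fold ratio.
- A plain landmark at 4 or 6 months, at doubling: 0.99-1.18.
- Time-dependent bevacizumab plus time-dependent progression, ratio 1 or 2: 0.98-1.03. Clock started at progression: also 0.98-1.03.
- With about 20-30% of users switching before documented progression, at doubling: 1.08-1.24 if they are left as not progressed, 0.93-1.01 if the switch date counts as progression, 0.99-1.01 if the clock starts at documented progression and they drop out.

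**Treatment HR (true 1.0) after ever/never adjustment.** It is 0.99-1.01 with equal uptake, 1.02-1.04 with uptake 10 points higher in the combination arm, 1.11-1.15 for 60% versus 30% (combination versus control), and 0.86-0.91 if reversed.

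**Lomustine.** Total doses as a fixed covariate, with inert doses, give HR 0.83-0.88 per dose. A time-dependent count plus progression gives 0.99-1.00. Biomarker response was not quantified.

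**The case against.** The models are exploratory and optional, and no decision uses them. The listed wording names a factor and does not forbid time-dependent coding. Both documents let additional exploratory analyses be described and justified in the SAP or the study report. So a reader should not infer that the plan prescribes ever/never coding: it prescribes none. What remains is that the factor is phrased as a yes/no status among baseline factors, that Protocol 12.2.4.2 makes its inclusion a commitment, and that the natural reading is biased.

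A reader might also infer that this covariate is the plan's only check on bevacizumab. It is not. SAP 6.9 notes that later anticancer therapy can lead to censoring, and SAP 6.10.4 leaves open alternative censoring dates. That route is optional and has its own bias. Listings and counts are planned as well.

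The size is open to challenge. Ratios of 1 or 2 imply that 11-32% of patients die without progressing. The RANO text in Protocol Attachment 5 counts clinical deterioration, and failure to return because of death or decline, as progression. Such deaths should then be fewer and the ratio higher, and at 5- to 10-fold they are 3-11%. This objection stands, which is why the ranges run to 10-fold. At 30% uptake with a 3- to 10-fold ratio, false significance is about 8-18%, so calling it frequent there is unsupported.

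Finally, the good performance of the recommended model comes from data without selection of fitter or sicker patients for bevacizumab. It shows that immortal time is removed, not that the estimate is causal.

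**Conclusion.** The concern holds as a gap worth closing in the exploratory OS models. The direction is firm: under ever/never coding an inert bevacizumab had an HR below 1 in every scenario. The size rests on assumed uptake, delay and effect of progression, and is about 0.50-0.90 over 10-60% uptake and a 1- to 10-fold ratio at a 0.7-month delay. False significance is common at 60% uptake, ranges from modest to substantial at 30%, and is near nominal at 10%, where the estimate is still biased.

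It would be wrong to conclude that the trial's main result is at risk. The Bayesian primary and secondary OS analyses do not use these covariates, nor does the futility rule. The adjusted treatment HR is distorted mainly if uptake differs between arms. The documents give no sign of such a difference, and the two lomustine arms are blinded to LY2157299 or placebo.

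**What to change.** Amend SAP 6.10.3 and 6.17, and Protocol 12.2.4.2 and 12.2.7:

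1. Restrict Cox models that report an adjusted treatment HR to baseline covariates.
2. Analyse poststudy bevacizumab in a separate model, time-dependent from its start date and together with time-dependent progression, or with the clock started at documented progression. Report how many patients switched before documented progression and how they were handled.
3. Code any other post-randomization covariate (lomustine exposure, biomarker response) as time-dependent.
4. Label these results as non-randomized and as covering the first post-study regimen only. Bevacizumab in a later regimen would be recorded as none, and no coding repairs that.

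The cost is a few sentences and modest programming. The PFS censoring rule already uses the date of subsequent therapy, so a start date should exist for the first regimen. Early switchers may lack a progression date because monitoring stops at new therapy, so they are either lost or approximated. Confounding by indication remains.

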6.10.4. Sensitivity Analyses

Additional analyses may be carried out to judge the influence of any patients who did not meet enrollment criteria but were inadvertently enrolled and continued on treatment after obtaining approval from the sponsor and/or patients who have continued treatment after objective disease progression. A subanalysis will be conducted by excluding such patients to determine their influence on the final study results.

Additional sensitivity analyses may also include the use of different censoring dates in the time-to-event analyses.

6.11. Health Outcomes/Quality-of-Life Analyses

Patients with at least baseline and 1 post-baseline assessment will be included in the analyses. Compliance with completing the questionnaires will be summarized at the group-level at each assessment period (defined as the number of completed or prorated questionnaires/number of expected questionnaires given those that are still on study).

Each health outcome parameter will be reported independently. Relationships (predictors or prognostic) among these parameters (patient reported symptoms and neurocognitive function) with other clinical parameters such as PS, OS, and disease assessments (based on MRI) may be explored. For example, relationship between change in neurocognitive function and prognostic and/or predictive nature of baseline assessments with OS or the relationship between change in neurocognitive function and change in MRI.

Health resource utilization such as use of psychostimulants, steroids, anti-epileptic medications, etc will be assessed by treatment arms and exploratory analyses adjusting for these covariates may be performed.

6.11.1. Neurocognitive Function

6.11.1.1. Neurocognitive Outcome Measures

Neurocognitive function will be measured by the HVLT-R, the Trail Making Test, Parts A and B, and COWA. These tests in the neurocognitive test battery will be completed at prestudy (baseline), end of cycle 1 (26 ± 2 days) and thereafter every 2 cycles starting at cycle 2 and after discontinuation of study therapy (Visit 801) during the study.

See table below for the administration time allocated to each test. The MDASI-BT, Trail Making Test Parts A and B, and COWA can be completed during the 20-minute wait before the delayed

recall for the HVLT-R; as a result of the delayed recall, the total time for administration of health outcome measures will be approximately 25 minutes.

Table JBAL.6.11. Cognitive Assessment Tests Used in Study H9H-MC-JBAL

Cognitive Domain	Test	Test Administration Time (minutes)
Memory	Hopkins Verbal Learning Test-Revised (HVLT-R)	5
Cognitive Processing Speed	Trail Making Test, Part A	3
Executive Function	Trail Making Test, Part B	5
Verbal Fluency	Controlled Oral Word Association (COWA)	5

Hopkins Verbal Learning Test-Revised (HVLT-R)

The patient is asked to recall a list of 12 words over 3 learning trials. After a 20-minute delay at the end of the third learning trial, the patient is asked to spontaneously recall the listed words (Delayed Recall trial) read in the 3 learning trials. The Delayed Recognition trial will follow immediately after the Delayed Recall trial and patient is asked to discriminate the listed words from amongst a set of distractors. The total time for this test, exclusive of the delay interval, is 5 minutes. There are 6 alternate forms of this test to minimize practice effects. The test measures learning and memory processes (Benedict et al. 1998).

The scoring for each of the 3 learning trials and the Delayed Recall trial is based on the number of correctly reported words in each trial. For the Delayed Recognition trial, scoring is based on the number of true-positives (listed words correctly recalled) and false-positives (listed words incorrectly recalled).

Four HVLT-R measures: Total Recall, Delayed Recall, Retention (%) and the Recognition Discrimination Index will be calculated based on the raw scoring from each trial. The total Recall score is the sum of three scores from the learning trials. The number of words correctly recalled during the Delayed Recall trial is the total score for Delayed Recall. The Retention score (percent retained) is calculated from the score of the Delayed Recall trial divided by higher of the two scores from the second and third learning trials. Lastly, the Recognition Discrimination Index is calculated by subtracting the total false positives score from the total true positives score.

Trail Making Test, Part A (TMTA)

This is a timed test of visual-motor cognitive processing speed, requiring the patient to connect dots in numerical order from 1 to 25 as fast as possible (Reitan 1992).

The measure of performance for this test is the time in seconds required to connect all 25 dots on the page.

Trail Making Test, Part B (TMTB)

This timed test is similar to Trail Making Test Part A, with the additional requirement of shifting mental set (an executive function). The patient connects dots alternating numbers and letters (ie. 1-A-2-B) as fast as possible (Reitan 1992).

The measures of performance for this test is the time in seconds required to connect the dots alternating numbers and letters on the page.

Controlled Oral Word Association (COWA)

This is a test of phonemic verbal fluency. The patient is asked to produce as many words as possible in 60 seconds beginning with a specified letter. There are 2 alternate forms of this test (Ruff et al. 1996).

Patients will be scored on the number of acceptable responses given on each letter and the sum of the number of acceptable responses from the 3 letters will be calculated as the patient's total score on the test.

A composite score, Clinical Trial Battery Composite (CTB COMP), will be calculated based on the standardized scores from the above tests. This is calculated as a sum of all the following 6 standardized scores (HVLT-R Total Recall + Delayed Recall + Delayed Recognition Discriminability+ TMTA + TMTB + COWA) and divide this by number of non-missing score to get the average standardized score.

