10.2.1. Neurocognitive Function

The healthcare professional (eg, nurse, psychologist) who is responsible for test administration in this study must complete training and follow administration procedures for the neurocognitive test battery. The tests in the neurocognitive test battery were selected because they are widely used standardized psychometric instruments that have been shown to be sensitive to the impact of cancer and the neurotoxic effects of cancer treatment in other clinical trials (Meyers and Brown 2006). The tests have published normative data that take into account age, and where appropriate, education and gender. The tests are given by the certified site administrators, and the total time for the cognitive assessment is approximately 20 minutes ([Table JBAL.10.2](#)). These neurocognitive function tests have been found to be a valid and feasible method in GB patients (Wefel et al. 2011).

Table JBAL.10.2. Cognitive Assessment Tests Used in Study H9H-MC-JBAL

Cognitive Domain	Test Administration Time (minutes)
Memory	
Hopkins Verbal Learning Test-Revised	5
Cognitive Processing Speed	
Trail Making Test, Part A	3
Executive Function	
Trail Making Test, Part B	5
Controlled Oral Word Association	5

Hopkins Verbal Learning Test-Revised

The patient is asked to recall a list of 12 words over 3 trials. After a 20-minute delay the patient is asked to spontaneously recall the list words (Delayed Recall) and discriminate the list words from amongst a set of distractors (Delayed Recognition). The total time for this test, exclusive of the delay interval, is 5 minutes. There are 6 alternate forms of this test to minimize practice effects. The test measures learning and memory processes (Benedict et al. 1998).

Trail Making Test, Part A

This is a timed test of visual-motor cognitive processing speed, requiring the patient to connect dots in numerical order from 1 to 25 as fast as possible (Reitan 1992).

Trail Making Test, Part B

This timed test is similar to Trail Making Test Part A, with the additional requirement of shifting mental set (an executive function). The patient connects dots alternating numbers and letters as fast as possible (Reitan 1992).

Controlled Oral Word Association

This is a test of phonemic verbal fluency. The patient is asked to produce as many words as possible in 60 seconds beginning with a specified letter. There are 2 alternate forms of this test (Ruff et al. 1996).

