6.11.1.2. Neurocognitive Analyses

Compliance rate will be calculated as the number of completed or prorated questionnaires divided by the number of expected questionnaires given those that are still on study. For Trail Making Tests A and B, patients with completed and prorated tests will be included in analysis. A test score can be prorated if test was discontinued or maximum time was used due to a neurological difficulty.

Each neurocognitive test will be converted to a standardized score (mean = 0, SD = 1) using published healthy control data. To prorate discontinued Trail Making Tests A and B, the raw scores will be divided by the number of circles correctly completed and then multiplying the resulting "time per circle" figure by 25. [Wefel et. al. 2011; Heaton RK et. al. 2004]. For each neurocognitive test, standardized scores will be summarized at each assessment. Repeated measures ANOVA will be performed for each measure to assess the mean differences in change from baseline standardized scores between treatment arms, adjusting for baseline score if needed. The change in standardized score from baseline will be calculated and using the Reliable Change Index (RCI) [Wefel et. al. 2011], the neurocognitive status over time will be categorized into improved, stable or decline. The RCI is a threshold that measures improvement or decline in neurocognitive function and represents a 90% confidence interval for the difference in raw score between baseline and the next assessment assuming no real change occurred. It is derived as follows:

$RCI = 1.64 (SEdiff)$ where $SEdiff = [2(SEM^2)]^{1/2}$ and $SEM = SD_1[(1 - r_{xy})^{1/2}]$

where $SEdiff$ is the standard error of difference in raw score from baseline to the next assessment, SEM is the standard error of measurement, SD is the standard deviation, and r_{xy} is the test-retest reliability statistic. All derived RCI will be rounded to the nearest whole number and compared with changes from baseline assessments to determine the change in neurocognitive status. Those changes that did not meet the RCI threshold will be considered stable performance. Any changes from baseline neurocognitive status showing improvement or decline will need to be confirmed at the next assessment if available. In the absence of a confirmatory assessment, any sign of improvement or decline in neurocognitive status will be deemed as stable.

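### The SAP misdefines HVLT-R recognition false positives as listed words; if programmed as written, the Recognition Discrimination Index would ignore accepted distractors

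*SAP*

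**What the plan says.** SAP 6.11.1.1 describes the HVLT-R as a 12-word list ("The patient is asked to recall a list of 12 words over 3 learning trials"). A delayed recall trial follows, and then a recognition trial in which the "patient is asked to discriminate the listed words from amongst a set of distractors". Protocol 10.2.1 describes the same task, to "discriminate the list words from amongst a set of distractors (Delayed Recognition", and gives no scoring rule.

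For the recognition trial the SAP states that "scoring is based on the number of true-positives (listed words correctly recalled) and false-positives (listed words incorrectly recalled". It then defines the summary measure: "the Recognition Discrimination Index is calculated by subtracting the total false positives score from the total true positives score". Neither document defines a false positive anywhere else.

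The recognition score is used further on. The Clinical Trial Battery Composite averages six standardized scores: "HVLT-R Total Recall + Delayed Recall + Delayed Recognition Discriminability+ TMTA + TMTB + COWA". I take the recognition term in that list to be the same index under a slightly different name. SAP 6.11.1.2 adds: "Each neurocognitive test will be converted to a standardized score (mean = 0, SD = 1) using published healthy control data".

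**The concern.** Throughout this part of the SAP, listed words are the targets read out in the learning trials, and they are set against the distractors. A listed word that the patient accepts is a true positive, and one that the patient rejects is a miss. Neither can be a false positive. The only written definition of the term therefore excludes the one response that an index of discrimination has to penalize: accepting a word that was not on the list.

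What is at stake is the scoring of one neurocognitive measure under the secondary health-outcomes objective. An index that cannot see accepted distractors would not match norms built for a discrimination score, so its standardized value would be wrong and would pass into the composite. SAP 6.11.1.2 also classes patients as improved, stable or declined by a reliable change index, separates decline on at least one test from stable or improved on all, and counts decline as a neurocognitive progression event. If the index is among the tests classified there, a misscored value could change a patient's category.

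**Working it through.** The plan gives no numerical score on this point, so there is no figure to reproduce. The check applies the stated formula under each possible meaning of false positive.

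Inputs:
- Listed words: 12 (SAP 6.11.1.1).
- Distractors, D: the SAP says only "a set of distractors". Assumed 6, 12 and 24 to show a range.
- Formula: index = true positives - false positives (SAP 6.11.1.1).

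Let h be the number of listed words accepted and f the number of distractors accepted. Misses are 12 - h.

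- Ordinary meaning (S), false positives = f: index = h - f.
- Literal reading A, a listed word answered wrongly, so false positives = 12 - h: index = h - (12 - h) = 2h - 12.
- Literal reading B, an empty category because an accepted listed word is always a true positive, so false positives = 0: index = h.

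Neither A nor B contains f.

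| Record | h | f | S (D = 6 / 12 / 24) | A | B |
|---|---|---|---|---|---|
| Perfect | 12 | 0 | 12 | 12 | 12 |
| Yes to every word | 12 | D | 6 / 0 / -12 | 12 | 12 |
| No to every word | 0 | 0 | 0 | -12 | 0 |
| 10 hits, no distractor accepted | 10 | 0 | 10 | 8 | 10 |
| 10 hits, half the distractors accepted | 10 | D/2 | 7 / 4 / -2 | 8 | 10 |
| 10 hits, 2 distractors accepted | 10 | 2 | 8 | 8 | 10 |
| 8 hits, no distractor accepted | 8 | 0 | 8 | 4 | 8 |

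Error of each literal reading against S:
- B - S = h - (h - f) = f. The score is too high by the number of distractors accepted.
- A - S = (2h - 12) - (h - f) = f - (12 - h), which is distractors accepted minus misses. The score can be too high (yes to every word: D - 0 = D), too low (8 hits, none accepted: 0 - 4 = -4) or correct (10 hits, 2 accepted: 2 - 2 = 0).

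Effect on the composite: an error of e points shifts the index by e/SD standard units, and the average of k non-missing scores by e/(k x SD), with k = 6 when all are present. The normative SD is not in the documents, so I give no figure in SD units.

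**The case against.** The best answer is that this is a slip in a parenthesis and not a chosen scoring rule. The term false positive, the distractor task, the subtraction and the name of the index all point to the ordinary meaning. Of the two literal readings, one makes the prescribed subtraction do nothing and the other relabels misses as false positives. The sentence also speaks of recall in a recognition trial, which suggests loose drafting. Protocol 10.2 says that details of test administration are supplied separately at training, Protocol 10.2.1 requires certified administrators, and the SAP cites the instrument's normative source.

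Most of this stands, and it rules out a stronger conclusion. A reader might infer that the plan leaves accepted distractors uncounted as a settled matter, so that the index no longer measures discrimination. The documents do not support that: they prescribe a subtraction of false positives, nowhere say that accepted distractors are left out, and do not show what was programmed. Nor do they support saying that every patient who accepts a distractor would be misscored (under reading A, 10 hits with 2 accepted gives the intended 8), or that memory decline would in general be recorded as stable. Total Recall, Delayed Recall and Retention are scored separately and are correct, and similar errors at baseline and follow-up would partly cancel in change scores.

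The objection does not remove the defect. Training and certification concern giving the test, not the SAP derivation. SAP section 3 assigns the standard tables, figures and listings to a contract organization, and its programmers should not have to override the only written definition.

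**Conclusion.** The definition is wrong as written and should be corrected; the harm depends on whether it was followed literally. If it was, the index does not depend on accepted distractors, and indiscriminate acceptance scores 12, the same as perfect performance, whatever the number of distractors. The intended score in that case is 12 - D, so the error is D points: 6, 12 or 24 for the assumed numbers. That record is an extreme; for other patients the error is f under reading B, or f minus misses under reading A. If the ordinary meaning was programmed, there is no error.

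The reach is limited to one of four HVLT-R measures and one of six composite components, plus the reliable-change analyses if the index is included in them. The comparison of overall survival is not touched.

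**What to change.** In SAP 6.11.1.1, replace the two parentheses so that the sentence reads: *true-positives (listed words correctly identified as listed words) and false-positives (distractor words incorrectly identified as listed words)*. Keep the index as true positives minus false positives. State the number of distractors and the resulting score range, and use one name for the index in both the measure list and the composite. Then check that the derivation specification and code follow this definition and match the scoring behind the published norms. The cost is one sentence of SAP text and a code check, with no new data.
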